12.3 DATA ANALYSIS

12.3.1 Data Monitoring Reports

The interim data monitoring reports will be prepared semi-annually and will include at a minimum the following tables:

 A summary of case and control recruitment and follow-up of cases according to sarcoidosis stage and Clinical Center, including the number of cases screened and recruited, the number of controls matched to cases, the number of cases at various
stages of follow-up, the number of completed scheduled visits for cases, and the number of study measurements or procedures completed for each study visit.

- 2. Tabulations of average number of specimens collected according to sarcoidosis category and Clinical Center, including the number of cases who completed each visit. Differences among sarcoidosis stages will be tested using significance levels developed without regard to a sequential monitoring plan.
- Longitudinal analyses of key exposure and outcome information by sarcoidosis category.
- Performance of required specimen collection and procedures and case compliance with scheduled return visits to the Clinical Centers.
- 5. Tabulations of the number of adverse events for required procedures for cases.
- 6. Number of cases screened, and proportion of cases screened who were eligible for ACCESS according to age, gender, race or other demographic characteristics. Number and proportion of cases screened and found ineligible according to the criterion or criteria for eligibility which resulted in their exclusion.
- Quality of submitted specimens to the central facilities and comparisons among clinics for key variable collection in ACCESS.

The content of each report will be discussed with the NHLBI Project Office staff and with the study leadership prior to preparation of the report and its distribution to the DSMB. Any other analyses requested by the NHLBI Project Office staff or the DSMB will be prepared and presented at the time of the DSMB meeting.

12.3.2 Analysis of the Case Control Study

12.3.2.1 Introduction

There has been extensive development of statistical methods for the analysis of case control studies. Most important for the proposed study are the regression methods as reported in Breslow and Day (Breslow and Day, 1980). There have been several reports about the importance of

including adjustment variables when performing case control analyses. Specifically, failure to include adjustment variables when performing case control analyses can lead to bias in estimating effects for other variables. Thus data analysis for case control studies is typically more complicated than analyses for clinical trials.

When performing an analysis of a case control study Breslow and Day report that confounding arises due to associations that cannot be removed by an appropriate study design alone. There are appropriate statistical methods (both parametric and non-parametric) that can be used to adjust for confounding effects in a case control design.

The first goal in a case control study is to fully understand the distributions of variables collected as part of the study, and how these variables may differ between cases and controls. As part of this understanding, detailed univariate analyses will be performed on each of the exposure variables collected in the case control study. These descriptive methods will include tabulations, presentation of means and standard deviations, and analyses for outlying observations. Frequently a categorization of a continuous variable may be beneficial in the conduct of a case control study since the exact nature of the risk relationship is unknown. Categorization allows flexibility in estimating a dose response relationship, and an easy way to visualize the data. It is recommended that this categorization should have more than two categories (preferably as many as five if sufficient data are available and natural divisions can be identified).

Once the data have been described, it will be important to develop analytical techniques that will allow for proper adjustment to control for confounding of observed results. Some methods for these analyses are presented below.

12.3.2.2 Matched Case Control Designs

Cases and controls will be matched with respect to the case's age (± five years), gender, and race. Random digit dialing may implicitly match cases and controls for geographical location. A matched design will be most appropriate for analyzing the data in this study. Simple presentations of matched case control data should follow the methods outlined by Breslow and Day. Categorical data will be presented using a cross tabulation of the number of cases exposed versus the number of controls exposed. Standard chi-square analyses will not be performed on these tables. Instead, methods for estimating the odds ratio from McNemar's test will be used to estimate the measure of association. Since the proposed number of cases is large, it will be possible to estimate 95% confidence intervals using the binomial approximation. For continuous variables, presentation of means will be accomplished using a paired t-test. These analyses can be performed using Proc Means in SAS. This will have the effect of adjusting for the matching variables. A point estimate for the difference in case and control means will be obtained and a 95% confidence interval for the difference will be calculated using this procedure.

It will be important to adjust study results for confounding variables that could bias the results of the case control study. Analyses using one more exposure variable(s) will be performed using conditional logistic regression methods. This method can be used to estimate odds ratios for casecontrol studies.

Statistical analyses for probability inference based on these estimates can also be performed using conditional logistic regression (Breslow et al, 1978). This model is robust in the sense that it will allow for the inclusion of effect modifiers or risk factors. Effect modifiers are variables that change the exposure-risk odd ratios for the disease. It will not be possible to estimate odds ratios for age, gender, or race since these are matching variables. However, it will be possible to include interaction terms between gender, race, or age and other exposure variables to determine if the odds ratio estimates for these other variables are homogenous in males and females or blacks and whites. In some situations, analyses will be required to determine if one type of exposure (e.g., occupational) is associated with a genetic predisposition of sarcoidosis. These analyses will be done using the conditional logistic regression model in a matched case control format. Tests of the effect modification of the exposure will be done using an interaction variable in the conditional logistic model. Conditional logistic regression will be performed using the PHREG procedure in SAS.

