3.6.4 Role of Mycobacterial Cell Wall Deficient Forms in Sarcoidosis

Since Schaumann's description of "peculiar corpuscles" present in the tissue of patients with sarcoidosis (Schaumann, 1941), an increasing body of evidence has implicated various infectious organisms, particularly mycobacteria, as the etiologic agent(s) in sarcoidosis. Judge, Graham, Khomenko, Barth and Almenoff (Judge and Mattman, 1976; Barth et al, 1979; Khomenko et al, 1987; Graham et al, 1988; Almenoff et al, 1996) have grown mycobacterial cell wall deficient forms (CWDF) from blood and tissue of patients with sarcoidosis. Approximately 80% of patients with sarcoidosis have had cultures positive for CWDF, and fewer than 15% of normal volunteers have had cultures positive for CWDF (Almenoff et al, 1996). However, conflicting results have been obtained using molecular biologic techniques to detect mycobacterial DNA in tissue, broncho-alveolar (BAL) fluid and blood of patients with sarcoidosis. In this study cultures for CWDF are made on 100 cases and 100 controls using techniques already established in the investigator's laboratory, and the species of organism(s) isolated are identified using molecular biologic techniques.

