12.2 POWER CALCULATIONS

12.2.1 Power Calculations for the Case Control Study

Determination of power for matched pair designs have been developed by Miettinen (Miettinen, 1969) and Walter (Walter, 1980) and more recently by Lubin, Gail, and Ershow (Lubin et al, 1988). These formulas can be used to evaluate the adequacy of the number of cases and controls in the case control design.

For binary exposure variables analyzed as part of the case control study the formula for power is the following:

power '
$$\ddot{O}\left(\frac{\ddot{a}@\hat{e}@N}{\sqrt{g @\hat{e}@(\hat{e}\%1) N/2}} \& Z_{\dot{a}}\right),$$

where $A_{\overline{k}}$ would be 1.96 ($\dot{a} = 0.05$ two sided test), N is the number of cases, \hat{e} is the number of controls matched to each case ($\hat{e} = 1$ in ACCESS), \ddot{a} is the difference between the expected percentages of cases and controls exposed to the risk factor of interest ($p_1 - p_0$) and \emptyset is the

proportion of case control pairs in which one person's exposure history differs from the other (discordance). Breslow and Day (Breslow and Day, 1980) have shown that only the discordant pairs in a case control study contribute information to the estimation of the odds ratio. Thus, discordant pairs are "informative".

Matched case control study analysis differs from prospective study or clinical trials data analysis. Psi (\emptyset) is dependent upon the degree of correlation between the probability that a case is exposed (has an attribute) and the probability that the control for this case is exposed. This correlation will be a function of the values of the matching covariates and thus the probabilities of exposure will vary from pair to pair and a correlation between these probabilities will be present.

Let p_1 be the expected percentage of exposure in the cases,

p₀ be the expected percentage of exposure in the control,

- and $Cov(p_1,p_0)$ be the expected covariance of the matched case and control exposure probabilities.
- then $\phi = p_1 + p_0 2 p_1 p_0 2 cov (p_1, p_0)$.

This can be rewritten to:

$$a' \frac{1\%\ddot{a}^2}{2} \& 2(p\&0.5)^2 \& 2cov (p_1, p_0)$$

with
$$\overline{p}' = \frac{p_1 \% p_0}{2}$$

Examination of this equation shows that \emptyset will generally be less than 0.55 except when \ddot{a} is very large, and/or the cov (p_1 , p_0) < 0. In general, matching produces positive correlations and it can be expected that there will be less than 55% of case control pairs that are informative.

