Tables 1 and 2 show the power of the proposed design to detect specified odds ratios as a function of the correlation (0.5 and 0.0) between case and control exposure rates, and the expected value of the control exposure rate with the alpha level for the test set at 0.05 (two sided test) and with 720 cases. With the proposed number of cases and controls there will be 98.6% power to detect odds ratios of 0.7 or less and 98.8% power to detect odds ratios of 1.4 or greater when the correlation between case and control exposures is 0.5 (Table 1) and the proportion of controls exposed is 0.3. If the correlation between cases and control exposures is 0.0 (a conservative estimate), the power is reduced to 84.3% and 85.1%, respectively. If the proportion of controls exposed is reduced to 0.05 there is at least 90% power to detect an odds ratio of 2.0.

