12.3.3 Analyses of ACCESS Substudies

All of the proposed analysis plans for the ACCESS Substudies are identical to the plans presented in Section 12.3.2. Only the sample sizes may change and this was addressed in Section 12.2.

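### Large-sample 95% intervals for the matched odds ratio are justified by the number of cases, but their adequacy depends on the discordant pairs, which can be few in rare-exposure tables and in substudies

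*Protocol*

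**What the plan says.** For categorical exposures, section 12.3.2.2 sets aside the ordinary chi-square analysis and states that "methods for estimating the odds ratio from McNemar's test will be used to estimate the measure of association". The interval follows from the size of the study: "Since the proposed number of cases is large, it will be possible to estimate 95% confidence intervals using the binomial approximation". It does not say which approximation is meant.

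Section 12.2.1, on power, states that "only the discordant pairs in a case control study contribute information to the estimation of the odds ratio" and that "it can be expected that there will be less than 55% of case control pairs that are informative".

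Section 12.3.3 gives the substudies the same analysis plan as section 12.3.2 and adds: "Only the sample sizes may change and this was addressed in Section 12.2". Section 12.2 deals with power and detectable effects, not with the validity of the interval. The substudies include two of 100 cases and 100 controls (sections 3.6.3 and 3.6.4). The power tables at the end of Chapter 12 go down to 50 pairs and to control exposures of 0.01 and 0.025.

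**The concern.** The matched odds ratio is the ratio of two counts: pairs in which only the case is exposed (b) and pairs in which only the control is exposed (c). A normal approximation needs both counts to be reasonably large. With 720 cases and a rare exposure, or with 100 pairs and a moderately rare one, one or both can be in single figures. The stated reason would therefore approve a large-sample interval in tables that do not support one. In a substudy the stated reason does not apply even on its own terms.

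At stake is whether intervals reported as 95% have that coverage, and whether they have a usable upper limit, for rare exposures and small laboratory substudies. Section 1.5.1 says that the etiology could include several low-prevalence agents, so such tables are within the study's purpose.

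**Working it through.** **Inputs from the Protocol.** Two-sided alpha 0.05 with 720 pairs: "with the alpha level for the test set at 0.05 (two sided test) and with 720 cases" (section 12.2.1). Correlation: "as a function of the correlation (0.5 and 0.0) between case and control exposure rates". Control exposures 0.01, 0.025, 0.05 and 0.1 and pair counts down to 50 come from Tables 1 to 12. The case of 180 pairs at 0.1 is in section 1.5.1, and 100 pairs in sections 3.6.3 and 3.6.4.

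**Reproducing the plan's figures.** With p1 = p0·OR/(1 + p0(OR − 1)) and ψ = p1 + p0 − 2p1p0 − 2r√(p1q1p0q0), where q = 1 − p, power = Φ(|p1 − p0|√N/√ψ − 1.96).

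- p0 = 0.05, OR 2, r = 0: p1 = 0.0952 and ψ = 0.1357, so power = Φ(0.0452 × 26.83/0.3684 − 1.96) = 0.909, as in Table 2.
- p0 = 0.3, OR 0.7 and 1.4: 0.986 and 0.988 at r = 0.5; 0.843 and 0.851 at r = 0. All four match section 12.2.1.

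**Expected discordant pairs are Nψ.** For 720 pairs, p0 = 0.01, OR 2, r = 0: p1 = 0.0198, ψ = 0.0198 + 0.01 − 0.0004 = 0.0294, and 720 × 0.0294 = 21.2. At r = 0.5, ψ = 0.0155, giving 11.2.

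**Coverage.** The number of discordant pairs n is Binomial(N, ψ), and b given n is Binomial(n, π), where π is the probability that a discordant pair has the case exposed. All tables with at least one discordant pair were enumerated. Each interval for π was converted by OR = π/(1 − π). A zero-width Wald interval (empty cell) counts as a miss. Unbounded means that the Wald limit for π reaches 1. OR 2 is the marginal value; at r = 0.5 the Protocol's convention implies a matched odds ratio of about 4.4.

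| Pairs, p0, r | Expected discordant | Wald coverage | Wald unbounded | c = 0 | Score (Wilson) | Exact |
|---|---|---|---|---|---|---|
| 720, 0.05, 0 | 97.7 | 0.943 | 0.000 | 0.000 | 0.951 | 0.961 |
| 720, 0.05, 0.5 | 51.7 | 0.929 | 0.014 | 0.000 | 0.952 | 0.968 |
| 720, 0.025, 0.5 | 27.2 | 0.911 | 0.262 | 0.007 | 0.951 | 0.972 |
| 720, 0.01, 0 | 21.2 | 0.922 | 0.070 | 0.001 | 0.952 | 0.971 |
| 720, 0.01, 0.5 | 11.2 | 0.848 | 0.714 | 0.126 | 0.957 | 0.987 |
| 180, 0.1, 0.5 | 23.4 | 0.905 | 0.370 | 0.013 | 0.951 | 0.975 |
| 100, 0.05, 0 | 13.6 | 0.904 | 0.216 | 0.010 | 0.952 | 0.977 |
| 100, 0.05, 0.5 | 7.2 | 0.721 | 0.839 | 0.263 | 0.952 | 0.989 |
| 50, 0.05, 0.5 | 3.6 | 0.466 | 0.900 | 0.501 | 0.936 | 0.992 |

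Mid-p coverage in these nine settings ranges from 0.951 to 0.985.

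**Cell wall deficient forms.** Section 3.6.4 reports "Approximately 80% of patients with sarcoidosis have had cultures positive for CWDF, and fewer than 15% of normal volunteers have had cultures positive". Taking 80% and 15% with independent exposures, the discordant probabilities are 0.80 × 0.85 = 0.68 and 0.20 × 0.15 = 0.03, so 100 pairs give an expected 68:3 table. There π̂ = 68/71 = 0.958 with standard error 0.0239. The Wald limits are 0.911 and 1.005: a lower odds ratio limit of 0.911/0.089 = 10.2 and no upper limit. The exact interval is 7.4 to 113, score 7.5 to 68, and log-odds-ratio 7.1 to 72. Over all samples, Wald coverage is 0.863 and 65% are unbounded, although c = 0 in only 5%. About 71 discordant pairs are expected, so the trouble here is a proportion near 1 and a small c, not a small total.

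**The case against.** The strongest reply is that the Protocol never specifies Wald. A score interval also counts as a binomial approximation, and it holds between 0.936 and 0.963 in every setting above. A log-odds-ratio interval holds 0.952 to 0.986 at OR 2 if tables with an empty cell are counted as covering. This stands: the under-coverage is conditional on one reading of an unnamed method. The log version is only a partial rescue, because it is undefined when a cell is empty. Counting those tables as failures gives 0.969 − 0.126 = 0.843 at 720 pairs, 1%, r = 0.5.

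Second, the sentence concerns simple presentations, adjusted analyses use conditional logistic regression, and the choice of interval is often left to an analysis plan. That lowers the weight of the point but does not remove it: the Protocol states a justification that its own section 12.2.1 contradicts and then extends the plan to the substudies.

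A reader might infer that the main study's intervals fail at the low prevalence on which it was designed. They do not. Section 1.5.1 names 5% exposure, where Wald with 720 pairs covers 94.3% or 92.9% and is unbounded in at most 1.4% of samples.

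A reader might also infer that exact intervals always give a finite upper limit. They do not: when no pair has only the control exposed, no method does, and at 50 pairs, 5%, r = 0.5 that happens in half of samples. Elsewhere most unbounded Wald limits come from the approximation, for example 71% against 13% with c = 0 at 720 pairs, 1%, r = 0.5.

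**Conclusion.** The point holds in a limited form. The justification by number of cases is wrong on the Protocol's own account, and extending the plan to substudies of about 100 pairs makes it weaker. The Protocol neither names the approximation nor provides for sparse tables.

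If plain Wald is used, the loss is material at 720 pairs with 1% exposure, at 100 pairs or fewer with 5% exposure, and in the cell wall deficient forms substudy at its quoted rates. It is moderate at 720 pairs with 2.5% exposure and at 180 pairs with 10% when r = 0.5 (about 91% in both), and minor at 720 pairs with 5% exposure. If a score interval is used, coverage is essentially preserved.

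The figures assume OR 2 and the Protocol's two correlations. The culture example instead assumes independence and takes 15% as the control rate, although the text gives it as an upper bound. The documents do not support a claim that the planned intervals are generally invalid.

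**What to change.** In section 12.3.2.2, replace the reference to the number of cases with the number of discordant pairs in each cell. Name the interval: the exact (Clopper-Pearson) or mid-p binomial interval on the discordant proportion, converted to the odds ratio, with the exact McNemar test. The simplest rule is to use it for every table. If a trigger is preferred, base it on the smaller discordant cell and not on the total: a rule such as fewer than 30 discordant pairs would miss the expected 68:3 table. Use exact conditional logistic regression for sparse models. When a discordant cell is empty, report a one-sided limit and say so.

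Repeat the rule in section 12.3.3 so that it governs the substudies. The cost is programming and slightly wider intervals, which mid-p keeps small. Design, recruitment and data collection do not change.

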2. Sarcoidosis patients (cases) are more likely to report employment in particular occupations or occupational categories immediately prior to diagnosis of their sarcoidosis conditions when compared to non-sarcoidosis referent group (controls).

3. Sarcoidosis patients (cases) are more likely to have a "dose-related" risk associated with their employment in particular occupational/industrial categories when compared with non-sarcoidosis referent group (controls), based on duration of employment.

Determination of whether or not there is an increased frequency in cases as compared to controls of history of exposures to infectious agents is an important objective of ACCESS. Sarcoidosis may represent a granulomatous response initiated by an environmental, occupational and/or infectious agent.

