6.3 CONTROL SELECTION

There is one population-based control group, selected for the study through random digit dialing. Controls are matched to cases on age (within five years), gender and self-designated race (black, white, other).

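### Age is wrongly listed with gender and race as having no estimable odds ratio: it is matched only within five years, so duration-of-employment analyses and age interactions lack an age main effect

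*Protocol*

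**What the plan says.** On matching, section 6.3 says "Controls are matched to cases on age (within five years), gender and self-designated race (black, white, other"). Section 12.3.2.2 repeats it: "Cases and controls will be matched with respect to the case's age (± five years), gender, and race". Sections 1.4 and 12.1 give the same five-year tolerance.

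On analysis, section 12.3.2.2 proposes a paired t-test for presenting continuous variables and says of it: "This will have the effect of adjusting for the matching variables". For adjusted analyses it specifies conditional logistic regression ("Conditional logistic regression will be performed using the PHREG procedure in SAS") and then states: "It will not be possible to estimate odds ratios for age, gender, or race since these are matching variables". The next sentence gives age a role only as an effect modifier: "However, it will be possible to include interaction terms between gender, race, or age and other exposure variables". Section 12.3.3 carries the same analysis plan over to the substudies.

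On exposures, section 3.3 includes a hypothesis of dose-related occupational risk "based on duration of employment".

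No section plans an age main effect or any other adjustment for the age difference that remains within pairs.

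**The concern.** A conditional likelihood loses a covariate only when that covariate is the same for both members of every pair. Gender and race category meet this condition by design. Age under a five-year tolerance does not, so the reason the protocol gives does not apply to it.

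Two analyses are affected. Years in an occupation accumulate with age, so if controls are on average somewhat older or younger than their cases, a duration comparison picks up part of that gap. An age-by-exposure interaction without its main effect is harmless for gender or race, but for age the product term can absorb residual age differences. Section 12.3.2.1 itself warns that leaving out adjustment variables can bias the effects of other variables.

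**Working it through.** **Inputs from the protocol.** 720 pairs (section 6.2); two-sided alpha 0.05 (section 12.2.1); age within five years; minimum age 18 (section 1.4).

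**Design check.** The section 12.2.1 formula, with one control per case, control exposure 0.3, odds ratio 0.7 and correlation 0.5:
- p1 = 0.21/0.91 = 0.2308; difference = 0.0692
- covariance = 0.5 × √(0.3 × 0.7 × 0.2308 × 0.7692) = 0.0965
- discordance = 0.2308 + 0.3 − 2(0.0692) − 2(0.0965) = 0.199
- power = Φ(0.0692 × √720/√0.199 − 1.96) = Φ(2.20) = 98.6%, as stated.

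The point below does not depend on this figure. It confirms the inputs.

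**Is the age effect estimable?** In 1:1 conditional logistic regression each pair contributes 1/(1 + exp(−βD)), where D is the case-minus-control difference. For gender and race D = 0 in every pair, so β disappears. For age D can lie anywhere from −5 to +5 years, so β is identified.

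**Interaction without a main effect.** Suppose both members of a pair are exposed (E = 1) and each person's own age is used. The exposure difference is 0, but the age-by-exposure difference is age(case) − age(control), so the interaction coefficient is partly fitted to the raw age gap. For gender the same product difference is 0. Using one age per pair, such as the case's, would avoid this; the protocol does not say which is meant.

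**Size for a continuous duration (assumed inputs).** Let g be the mean age gap, a the exposure-years accrued per year of age, and s the exposure SD, with no true effect and no within-pair correlation. Then bias = g × a/s in SD units, z shift = bias × √(720/2) = 18.97 × bias, and rejection = Φ(shift − 1.96) + Φ(−shift − 1.96).

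| Gap (years) | Accrual | SD (years) | Bias (SD) | z shift | Rejection |
|---|---|---|---|---|---|
| 0 | any | any | 0 | 0 | 5% |
| 0.25 | 0.5 to 1 | 8 | 0.0156 to 0.0313 | 0.30 to 0.59 | 6% to 9% |
| 0.5 | 0.5 to 1 | 8 | 0.0313 to 0.0625 | 0.59 to 1.19 | 9% to 22% |
| 1 | 0.5 to 1 | 8 | 0.0625 to 0.125 | 1.19 to 2.37 | 22% to 66% |
| 1 | 0.05 to 0.1 | 3.9 | 0.013 to 0.025 | 0.24 to 0.48 | 6% to 8% |

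The last row is a rarely held occupation: 10% ever employed, mean 10 years and SD 8 among them. The population mean is then 1, the variance 0.1 × (64 + 100) − 1 = 15.4, and the SD 3.9. Positive within-pair correlation would raise all the shifted rates.

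**Size in the conditional logistic model (simulation).** 720 pairs, 1,500 repetitions per setting. Assumptions: case ages 18-75, mean about 42; control ages drawn within five years and at least 18; duration a random fraction (mean 0.75) of years since 18; no true effect.

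| Mean case-minus-control gap (years) | OR per 10 years, age omitted | Rejection | OR, age included | Rejection |
|---|---|---|---|---|
| 0.0 | 0.99 | 5% | 0.99 | 4.5% |
| −0.25 | 0.90 | 12% | 1.01 | 3.6% |
| −0.5 | 0.80 | 40% | 1.00 | 3.9% |
| −1.0 | 0.65 | 91% | 1.00 | 4.1% |
| +0.5 | 1.25 | 39% | 1.00 | 5.0% |

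The age coefficient was estimated with a standard error of about 0.028 to 0.030 per year; the SD of the within-pair age difference was about 2.8 to 2.9 years. The age floor of 18 alone, with otherwise evenly spread control ages, produced a gap of only about −0.01 year.

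**The case against.** A reader might infer that the protocol bars age from the model. It does not. It says that an odds ratio for age cannot be estimated, and it admits age in interactions; only the main effect is ruled out. There is also a sensible reading in which the authors mean that matching makes age uninterpretable as a risk factor. That is true, but it does not make the coefficient inestimable or unnecessary for adjustment.

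The protocol also calls for adjustment for confounders and gives no closed covariate list, so a later analysis plan could add age. The paired t-test is offered for presenting means, with adjusted work left to regression. Both points soften the concern. Neither corrects a stated reason that would lead an analyst to leave the age main effect out.

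The strongest objection is to the size. The tolerance is symmetric and no section reports a directional gap. The highest rates need a full one-year gap and an exposure that nearly everyone accrues for much of adult life, whereas section 3.3 concerns particular occupations, many of them uncommon. That stands, and it is why the range begins near 5%. Section 11.4 mentions reference dates for controls, but the protocol does not say how they bear on the age gap.

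**Conclusion.** The statement is wrong for age and should be corrected. The consequence is possible, not established. A reader might infer that the duration analyses will be biased, or that 22-66% is the expected false-positive rate. The documents support neither: that range rests on the assumed one-year gap, 0.5-1 year accrual and SD of 8 years, and the simulated 91% on an exposure held for about three-quarters of adult years. With a 0.25-year gap, or a rarely held occupation, the first calculation gives about 6-9%. With no gap there is no bias, only some lost precision.

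Nor does the argument reach every exposure. Duration of employment is the only explicitly cumulative hypothesis. Tobacco and rural residence are listed without a cumulative measure, and the mechanism does not directly apply to genetic markers.

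**What to change.** - In section 12.3.2.2, limit the sentence on odds ratios that cannot be estimated to gender and race, and say that pairing adjusts for age only to within five years.
- Enter continuous age, at the reference date, as a main effect in conditional logistic models of duration of employment or any other cumulative exposure, and wherever an age interaction is fitted.
- For continuous cumulative exposures, supplement the paired t-test by regressing the within-pair exposure difference on the within-pair age difference and testing the intercept.
- State that the age coefficient is an adjustment term, not an estimate of age as a risk factor.

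Age is already collected. The cost is one degree of freedom per model and a little programming. Models of genetic markers need no change on this account unless they include an age interaction.
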